# 5 Data Sets for Analysis and Missing Data

## 5.1 Data Sets for Analysis

The following analysis datasets are defined for this trial:

Enrolled Sample – all subjects enrolled in the trial.

- Randomized Sample all subjects allocated based on the randomization process and recorded in the database. Subjects treated without being randomized will not be considered as randomized and therefore will not be included in any efficacy or safety population analyses.
- Safety Sample all randomized subjects who receive at least 1 occurrence of either CT-152 or sham use. All safety assessments will be performed on the safety analysis set. If any subjects receive a treatment that differs from the assigned treatment, then the safety analyses will be conducted on the treatment actually received.
- FAS Sample all randomized subjects who receive at least 1 occurrence of either CT-152 or sham use, and have baseline and at least 1 postbaseline assessment of MADRS total score. Subjects included in FAS Sample are defined as evaluable subjects.
- Per-protocol (PP) Analysis Sample all subjects in the FAS Sample who were treated for 6 weeks, did not have a major protocol deviation, and were adherent to CT-152 or sham treatment in this trial. The classification of protocol deviations will be established in a blinded review by the sponsor in a meeting prior to breaking the blind. Specifically, the following criteria will be used to exclude subject from PP analysis sample.
  - 1. Subjects in the FAS Sample but not treated for 6 weeks

- 3. Subjects who reported concomitant medication use that will impact the primary efficacy and key secondary endpoints
- 4. Subjects who had major protocol deviation that will impact primary efficacy and key secondary endpoint
- 5. Subject who received the wrong study digital therapeutic

The PP Analysis Sample will only be used for sensitivity analysis of the primary efficacy and key secondary variables.

The core dataset for all efficacy analyses is the FAS Sample, which is created based on the intent-to-treat (ITT) principle. However, as will be described below, in order to handle missing data and restrictions imposed by different types of analyses (e.g., change from baseline analysis), other datasets derived from the FAS dataset will be used for the efficacy analyses.

#### 5.2 Handling of Missing Data

The MADRS is utilized as the primary efficacy assessment of a subject's level of depression. The MADRS consists of 10 items, all rated on a 0 to 6 scale with zero being the "best" rating and 6 being the "worst" rating. The MADRS total Score is the sum of ratings for all 10 items; therefore, possible total scores range from 0 to 60. The MADRS total Score will be unevaluable if less than 8 of the 10 items are recorded. If 8 or 9 of the 10 items are recorded,

the MADRS total Score will be the mean of the recorded items multiplied by 10 and then rounded to the first decimal place.

The mixed-effect model repeated measure (MMRM) assumes data are missing at random (MAR), which is a reasonable assumption in longitudinal clinical trials in MDD. However, the possibility of "missing not at random" (MNAR) data can never be ruled out. As sensitivity analyses, selection model, pattern-mixture model, and/or shared parameter model will be used to explore data missing mechanisms of MNAR and investigate the response profile of dropout patients by last dropout reason under MNAR mechanism for the following 3 scenarios: 1) Dropout reasons due to either adverse event (AE) or lack of efficacy (LOE) as MNAR, 2) Dropout reasons due to either AE or LOE or subject withdrew consent as MNAR, 3) All dropouts as MNAR using both 1) Delta adjustment imputation method which is to departure from MAR assumption by progressively increasing the delta until conclusion from the primary analysis is overturned, and 2) Placebo based imputation methods in which missing data for both sham and CT-152 group are imputed based on the imputation model derived from sham data. If CT-152 improved outcomes prior to dropout, this benefit is carried into subsequent imputed values, but will diminish over time in accordance with the correlation structure. Details are provided in Section 8.1.3 Sensitivity Analysis.

The observed-cases (OC) data set will consist of actual observations recorded at each scheduled visit during the treatment period and/or extension period and no missing data will be imputed. MMRM, Wu-Bailey, and pattern-mixture model will be performed on the OC dataset.

The last-observation-carried-forward (LOCF) data set will include data recorded at a scheduled visit during or, if no observation is recorded at that visit, data carried forward from the previous scheduled visit. For the treatment period, baseline data will not be carried forward to impute missing values. For the extension period, the only imputation will be applied to Week 10 data. If no observation is recorded at Week10, available observations from Week 8 will be carried forward. Week 6 data will not be carried forward to impute missing values at Week 8. The analysis of covariance (ANCOVA) analysis will be primarily performed on the LOCF data. The model will include treatment and study center as main effects, and baseline value as a covariate. The ANCOVA analysis will also be applied on the OC dataset, where study center will not be included in the model.

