6.1.2 Antidepressant Therapy

To qualify for this trial, subjects must have received adequate treatment (ie, minimum therapeutic dose or higher) with a permitted ADT in the current episode for at least 6 weeks prior to screening. The medications listed in Section 6.5.2 are considered permitted ADT. Additionally, the subject must have received the same dose of their current monotherapy ADT for at least 4 weeks prior to baseline (Day 1). Subjects who are taking ADTs other than the permitted ADTs will not be eligible for the trial.

Subjects who are eligible for randomization will be randomized into the trial and will receive either CT-152 or sham in addition to their current ADT during the treatment period. During the extension period, subjects will continue their ADT.

Subjects must remain on the same ADT and should remain on the same dose for the duration of their participation in the trial. However, if the principal investigator or designee determines that dose adjustments to ongoing ADT must be made for tolerability reasons, this requires discussion with the medical monitor to document the reason for the change. In all cases, the specific ADT cannot change before the end of the trial and at all times the dose of permitted ADT must remain within the therapeutic range specified in the drug label. If subjects cannot tolerate the minimum therapeutic dose of ADT they must be discontinued.

Subjects required to change from one ADT to another, or who require augmentation with additional pharmacotherapy or psychotherapy as part of ongoing clinical care during the course of the trial, must be withdrawn. Additionally, treatment with more than one ADT during the trial, or other pharmacological augmentation, is not permitted.

Subjects are expected to maintain the ADT formulation identified at trial entry (ie, generic or branded) throughout their participation in the trial. The supply for the ADT can be provided by the sponsor via a mail order pharmacy or the subject can continue to take ADT that was previously prescribed before trial entry.

If the subject does not continue to take ADT from the supply that was previously prescribed before trial entry, the ADT will be prescribed by the principal investigator or designee and filled by a mail order pharmacy and delivered to the subject's home. Details are provided in the Site Operations Manual.

Protocol No. 345-201-00002

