Where $\Delta\mu$ WHODAS 2.0 CT-152+ADT and $\Delta\mu$ WHODAS 2.0 sham+ADT are the changes from baseline in Week 6 on the WHODAS 2.0 total score in CT-152+ADT and sham+ADT treatment groups, separately.

Change from screening to Weeks 4 and 6, separately, on the PHQ-9 total score will be analyzed using the same method as in the primary analysis with a replacement of the interaction term of visit by screening PHQ-9 total score as a covariate. The hypothesis tested is the null hypothesis that the change from screening to each schedule week (Weeks 4 and 6) in the PHQ-9 total score using CT-152+ADT is equal to the change from screening to each schedule week (Weeks 4 and 6) in the PHQ-9 total score using the sham+ADT.

 H_0 : $\Delta \mu_{PHO-9\ CT-152+ADT} = \Delta \mu_{PHO-9\ sham+ADT}$

 $H_A\text{: }\Delta\mu\text{ }_{PHQ\text{--}9\text{ }CT\text{--}152\text{+}ADT} \neq \Delta\mu\text{ }_{PHQ\text{--}9\text{ }sham\text{+}ADT}$

Where $\Delta\mu_{PHQ-9\ CT-152+ADT}$ and $\Delta\mu_{PHQ-9\ sham+ADT}$ are the changes from screening to Weeks 4 and 6 in PHQ-9 total score in CT-152+ADT and sham+ADT treatment groups, separately.

Partial response on the MADRS is defined as \geq 30% and < 50% reduction in MADRS total score from baseline. Partial response rates at Weeks 2, 4, and 6, separately, will be analyzed using the same statistical model for MADRS response.

 H_0 : $\pi_{CT-152+ADT} = \pi_{sham+ADT}$

 H_A : $\pi_{CT-152+ADT} \neq \pi_{sham+ADT}$

[figure not shown]
Protocol No. 345-201-00002

Where $\pi_{\text{CT-152+ADT}}$ and $\pi_{\text{sham+ADT}}$ are the MADRS partial response rates at Weeks 2, 4, and 6 in CT-152+ADT and sham+ADT treatment groups, separately.

Response on the MADRS during the extension period is defined as full or partial, defined as $\geq 30\%$ reduction in MADRS total score from baseline. Response rates at Weeks 8 and 10, separately, will be analyzed using summary statistics in LOCF analysis.

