# 8 Efficacy Analysis

All efficacy analyses pertaining to the treatment period and extension period will be performed on the FAS Sample, and patients will be included in the treatment group as randomized.

Statistical comparisons are based on 2-sided, 0.05 significance levels.

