# 8.3 Other Efficacy Endpoints

Other efficacy analyses are listed below. All other efficacy endpoints will be evaluated at a nominal 0.05 level (2-sided) without adjusting for multiplicity.

- 1) Change from baseline to Weeks 2 and 4 in the MADRS total score
- 2) Change from baseline to Weeks 2 and 4 in the GAD-7 total score
- 3) Change from baseline to Weeks 2, 4, and 6 in the CGI-S score.
- 4) Change from screening to Weeks 4 and 6 in the PHQ-9 total score.

- 5) Change from baseline to Week 6 in the WHODAS 2.0 total score.
- 6) MADRS response at Weeks 2, 4, and 6, where response is defined as ≥ 50% reduction in MADRS total score from baseline
- 7) MADRS partial response at Weeks 2, 4, and 6, where partial response is defined as ≥ 30% and < 50% reduction in MADRS total score from baseline
- 8) MADRS response at Weeks 8 and 10 , where response is defined as full or partial, and defined as  $\geq$  30% reduction in MADRS total score from baseline.

Endpoints (1) through (4) will be evaluated using the same MMRM model described in the primary analysis. The LOCF and OC analyses using ANCOVA will also be conducted. The LOCF analysis model includes treatment and trial site as main effects, and baseline value as covariate. For the OC analyses, trial site will not be included in the model.

Endpoint (5) will be evaluated using ANCOVA with baseline as covariate and treatment and, in LOCF analyses, trial site as main effects. Endpoints (6) through (7) will be evaluated by Cochran-Mantel-Haenszel (CMH) General Association Test controlling, in LOCF analyses, for trial site. OC analyses will also be conducted for variables (5) through (7) but will not control for trial center.

Endpoint (8) will be analyzed using descriptive statistics on LOCF dataset.

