# 4 Supportive Analyses for Assessment for Durability Based on MADRS Total Score

The following endpoints from Section 8.3 (Other Efficacy Endpoints) CC in the original SAP will be served as supporting evidence to the durability of effect assessed based on MADRS total score. They will be analyzed by the same statistical model as used for Endpoints (2) - (4) in Section 3 of this addendum.

- 1) MADRS full response at Weeks 8 and 10
- 2) MADRS partial response at Weeks 8 and 10
- 3) MADRS remission at Weeks 8 and 10

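### MADRS response at Weeks 8 and 10 is labelled LOCF on the FAS, but subjects with no MADRS from Day 49 have no value, so Week 8 is in effect observed-case and can rest on different subjects from Week 6

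*SAP*

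**What the plan says.** **Analysis set.** SAP 8: "All efficacy analyses pertaining to the treatment period and extension period will be performed on the FAS Sample".

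**Treatment-period LOCF.** Under SAP 5.2 a missing visit takes "data carried forward from the previous scheduled visit", and baseline is never carried. SAP 8.3 analyses full and partial response at Weeks 2, 4 and 6 on these data with a CMH test stratified by site.

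**Extension LOCF.** The same section allows one imputation: "If no observation is recorded at Week10, available observations from Week 8 will be carried forward". It then rules out the other: "Week 6 data will not be carried forward to impute missing values at Week 8".

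**Extension response endpoints.** Protocol 9.4.1.2.3, for response of at least 30%: "Response rates at Weeks 8 and 10, separately, will be analyzed using summary statistics in LOCF analysis". SAP 8.3: "Endpoint (8) will be analyzed using descriptive statistics on LOCF dataset". Section 4 of the SAP Addendum names full response, partial response and remission at Weeks 8 and 10 as supporting evidence for durability: "They will be analyzed by the same statistical model as used for Endpoints (2) - (4) in Section 3 of this addendum". Addendum 1 leaves all other conventions unchanged, so SAP 5.2 still governs.

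**Visit mapping.** SAP 10.1 assigns scheduled and early termination assessments by study day: Week 6 is Days 35–48, Week 8 is Days 49–62 and Week 10 is Days 63–77.

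**The concern.** Response rates at Weeks 6, 8 and 10 invite reading in sequence, as response gained and then held. They carry one label (LOCF) and one analysis set (FAS), yet the rules underneath differ. At Week 6 a subject who has left is kept through the last postbaseline score. At Week 8 the same subject has no score at all.

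Loss before Week 8 need not be unrelated to outcome. Subjects who change antidepressant, or "who require augmentation with additional pharmacotherapy or psychotherapy as part of ongoing clinical care during the course of the trial, must be withdrawn" (Protocol 6.1.2). Worsening depression (6.5.3), prohibited treatment (6.5.1), lack of efficacy and adverse events (7.3.3) are further routes out. SAP 8.1.3.1 itself accepts that dropout for adverse events or lack of efficacy may be missing not at random. If such subjects are unscored, response can look sustained partly because non-responders are no longer counted, and unequal loss between arms would distort the comparison.

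**Working it through.** **1. Who is unscored.** Take a FAS subject whose last MADRS is on or before Day 48.
- Week 6: scored, by observation or LOCF. The exception is a subject whose only postbaseline scores are removed by the SAP 10.1 rule on assessments made more than seven days after last use of the application.
- Week 8: nothing in Days 49–62, and carrying Week 6 is barred. No value.
- Week 10: nothing in Days 63–77 and no Week 8 value to carry. No value.

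A subject with an early termination MADRS on Days 49–62 is scored at Week 8 and carried to Week 10. The unscored group is therefore those with no MADRS from Day 49, not everyone who leaves before the Week 8 visit.

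**2. What the label means.** With no imputation into Week 8, the LOCF and observed-case data at Week 8 are identical. An observed-case companion analysis would differ only in dropping site from the CMH test. Week 10 adds only carried Week 8 values.

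**3. The denominator.** No section gives one for subjects without a value. A CMH test needs a class for each subject, and none is assigned to the unscored. SAP 5.1 expects data sets derived from the FAS to be used because of missing data. The natural reading is that unscored subjects drop out, but it is not stated.

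**4. Size of the effect on a rate.** The plan's own sample size reproduces: a 3-point difference, SD 9, two-sided alpha 0.05 and 85% power give 162 per arm, 324 in total, and 324/0.90 = 360. That 10% allowance is for failing to enter the FAS; it is not a rate of loss before Week 8, and the documents give none. What follows therefore rests on assumed rates, with 162 FAS subjects per arm.

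Let d be the share unscored, p the response rate among scored subjects and q the rate among unscored subjects.
- Scored-only rate = p
- Whole-FAS rate = (1 − d)p + dq
- Overstatement = d(p − q)

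With q = 0 and whole-subject counts:

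| Nominal d | Unscored of 162 | p = 40% | p = 60% |
|---|---|---|---|
| 5% | 8 | 2.0 points | 3.0 points |
| 10% | 16 | 4.0 | 5.9 |
| 20% | 32 | 7.9 | 11.9 |
| 25% | 40 | 9.9 | 14.8 |

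The sign depends on q. At d = 10% and p = 50%, the whole-FAS rate is 47.0% if q = 20% (overstated by 3.0 points), 50.0% if q = 50% (no bias) and 53.0% if q = 80% (understated by 3.0 points).

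**5. Effect on the arm difference.** Assume scored rates of 55% on CT-152 and 45% on sham, a difference of 10.0 points. Counting unscored subjects as non-responders:
- 20% unscored on CT-152, 10% on sham: 0.55 × 0.80 − 0.45 × 0.90 = 3.5 points
- 10% on both: 0.55 × 0.90 − 0.45 × 0.90 = 9.0 points
- 10% on CT-152, 20% on sham: 0.55 × 0.90 − 0.45 × 0.80 = 13.5 points

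**6. Planned safeguards.** The delta-adjusted and placebo-based imputations in SAP 8.1.3.1 are set out for the primary MADRS change. They do not reach response at Weeks 8 and 10.

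**The case against.** The rule is explicit and has a good reason behind it. Carrying an on-treatment Week 6 score into the extension would assume the durability under assessment. That stands, and carrying Week 6 forward is not the remedy.

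The denominator is an inference. If the descriptive rates use the FAS count, unscored subjects already count as non-responders and there is no overstatement against that standard. This also stands, but the intention would need writing down, and it would not settle how the CMH test classes these subjects.

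The stakes are limited. The durability criterion is the MMRM point estimate of MADRS change (SAP 8.2.1), and the response rates are supportive and tested at a nominal level (Addendum 2). SAP 6.1 already reports completion and reasons for discontinuation by arm, though not the number unscored at each extension visit. Part of the source for the Addendum endpoints is blacked out and remission is not in the visible SAP 8.3 list, so any handling specific to remission cannot be checked.

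Two stronger readings are tempting. A reader might infer that the extension figures are completer rates. They are not: Protocol 4.5 defines completers by the Day 70 assessments, whereas Week 10 also includes subjects with only a Week 8 or early termination value. A reader might also infer that most unscored subjects are treatment failures. Protocol 7.3.3 also lists technical problems, loss to follow-up, protocol deviation, site termination and withdrawal by the subject, and nothing shows which reasons will dominate.

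**Conclusion.** The gap is real, in a limited form. FAS subjects with no MADRS from Day 49 have a Week 6 response status (apart from the seven-day exception) but none at Week 8 or 10, so full response, partial response, response of at least 30% and remission can rest on different subjects at Week 6 and in the extension. Week 8 is observed-case under an LOCF label.

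The overstatement is conditional: it arises if rates are taken over scored subjects and the unscored respond less often. It is then about 2–3 points at 5% unscored and 10–15 points at 25%, assuming p of 40–60% and q of 0. A reader might infer that the plan does overstate durability, or that it favours CT-152. The documents support neither, since they give no loss rates and the arm contrast can narrow or widen. Nor does the point touch the MMRM durability criterion. It is a cheap improvement to supportive evidence.

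**What to change.** In SAP 5.2, SAP 8.3 endpoint (8) and Addendum 4:

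1. State the denominator for every Week 8 and Week 10 response endpoint, and label the Week 8 analysis as observed-case.
2. Add a sensitivity analysis on the whole FAS at Weeks 6, 8 and 10 under one common rule: a subject with no MADRS in the visit window counts as a non-responder (for remission, not in remission; for partial response, not a partial responder). Week 6 must be included. Applying the rule only in the extension, with Week 6 left on LOCF, would keep the visits non-comparable and tilt them towards apparent loss of response.
3. Report the number unscored at each visit by arm and reason.

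The existing analysis can stay. The cost is SAP wording and one more table, in which subjects lost for unrelated reasons count as failures; the counts by reason let a reader judge how far that matters.

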# 6 Study Conduct

# 6.1 Subject Disposition, Completion Rate, and Reasons for Discontinuation

Subject disposition will be summarized on the Randomized Sample by treatment group and by center.

Subject completion rate and reasons for discontinuation will be summarized on the Randomized Sample by treatment group.

## 6.2 Adherence to Digital Therapeutic

Adherence data to digital therapeutic use in the treatment period will be analyzed on Safety Sample by treatment group. Number and percentage of subjects will be summarized based on the number of treatment sessions they complete Mean, range, and standard deviation of the number of treatment sessions completed will also be provided. The listing of protocol adherence by subject will be provided.

#### 6.3 Protocol Deviation

Protocol deviations including the types of deviations will be summarized by center and treatment group on Randomized Sample. Listing of protocol deviations will be provided.

#### 7 Baseline Characteristics

#### 7.1 Baseline Definition

For the variables which are collected at baseline, the baseline is the Baseline measurement (expected to be at Day 1). Baseline measurement is defined as the last available measurement prior to the start of intervention with double-blind digital therapeutic (CT-152 or sham) in the treatment period.

#### 7.2 Demographic Characteristics

Baseline demographic characteristics include age, sex, race, and ethnicity. For the Randomized Sample, demographic characteristics will be summarized by treatment group using the descriptive statistics. Mean, range, and standard deviation will be used to describe continuous variables such as age. Frequency distributions will be tabulated for categorical variables such as race.

## 7.3 Medical and Psychiatric History

A summary of medical and psychiatric history will be presented on the Randomized Sample by treatment group and overall. Listings of medical and psychiatric history will be provided.

#### 7.4 Neuropsychiatric Diagnosis

A summary of MINI International Neuropsychiatric Interview (M.I.N.I.) will be presented on the Randomized Sample by treatment group and overall. The number and percentage of patients who meet each diagnosis criteria, and the number and percentage of patients with each primary diagnosis will be summarized.

## 7.5 Baseline Psychiatric Evaluation

For the Randomized Sample, baseline psychiatric scale evaluation will be summarized by treatment group and overall. The mean, median, range and standard deviation will be used to summarize the assessments of: MADRS total score, GAD-7 total score, CGI-S score, and WHODAS 2.0 total score. Descriptive statistics of PHQ-9 total score, and CCI at screening visit will also be provided.

